#### **16a-Allocation concealment mechanism**

- The two groups will be treated will be equally prepared for surgical procedure. Then the decision of which group will receive CAF+SCTG and which will receive CAF+SCTG combined with PRF will be selected according to the randomized numbers placed in opaque sealed envelopes. The number will be picked by participant.

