#### **16-Allocation**

Patients will be randomly allocated using computer generated randomization ([www.randomizer.org](http://www.randomizer.org)) and will be performed by [name]. The numbers will be allocated to each patient.

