**16b-Implementation:**

- All patients who give consent for participation and who fulfill the inclusion criteria will be randomized.
- Randomization will be performed by [name] who is neither involved in the treatment nor in the outcome measurements.

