**17-Blinding**

- Blinding of the participants and operator is not applicable because of the nature of the treatment.
- Outcome assessor will be blinded.
- The biostatistician will be blinded.

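### The participant picks the allocation number, so the assignment is not tied to the computer list in enrolment order and a redraw after opening could not be checked

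*Combined protocol and SAP*

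**What the plan says.** All references are to the combined protocol and SAP.

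- Section 16 (Allocation): "Patients will be randomly allocated using computer generated randomization", using a web randomiser, and "The numbers will be allocated to each patient".
- Section 16a (Allocation concealment mechanism): "The two groups will be treated will be equally prepared for surgical procedure. Then the decision of which group" gets which treatment is "selected according to the randomized numbers placed in opaque sealed envelopes". The section ends: "The number will be picked by participant".
- Section 16b (Implementation): "Randomization will be performed by" a named person "who is neither involved in the treatment nor in the outcome measurements".
- Section 17 (Blinding): "Blinding of the participants and operator is not applicable because of the nature of the treatment". The outcome assessor and biostatistician are to be blinded.
- Section 13 (Participant timeline) puts baseline recession depth at T1, and allocation and intervention together at T2.
- Section 15 (Recruitment strategy) describes consecutive sampling. Section 23 (Auditing) says that there will be none.

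**The concern.** Sections 16 and 16a describe two ways for a number to reach a patient. If the list assigns the numbers, there is nothing to pick. If the participant picks, the list fixes the contents of the envelopes but not which patient receives which one.

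This matters because a list opened in order sets an expected assignment for every patient in advance, and a free pick does not. If an envelope were opened, disliked and exchanged for another, the final set of assignments would look as valid as any other. Operator and participant both learn the assignment, so either could have a preference. An imbalance created in this way enters the primary comparison before treatment starts, and a blinded assessor cannot remove it.

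**Working it through.** **The plan's own sample size.** Inputs from section 14 (Sample size): difference 0.45 mm, ±0.38 mm read as the SD, power 80%, significance level 5%. Section 20 (Statistical method) makes tests two-tailed.

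- Normal approximation: n = 2 × [0.38 × (1.960 + 0.842) / 0.45]² = 11.19, so 12 per group, as stated. The t-test version gives 12.23, with power 79.2% at 12.
- Non-parametric allowance: 12 × 1.15 = 13.8, or 12 / 0.864 = 13.9. Either rounds up to 14.
- Losses: no rate is stated. With 15%, 14 / 0.85 = 16.5, so 17.

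The figures reproduce, and this point does not change them. They supply 17 per arm (34 in total) and the 0.45 mm target.

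**What would make the assignment checkable.**

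| Element | Stated? |
|---|---|
| Computer-generated numbers | Yes, section 16 |
| Opaque, sealed envelopes | Yes, section 16a |
| Randomiser outside treatment and measurement | Yes, section 16b |
| Baseline measured before allocation | Yes, section 13 |
| Sequentially numbered envelopes | No |
| Opening in enrolment order | No; section 16a has the participant pick |
| First pick is final | No |
| Who holds and opens the envelopes | No |
| Log of openings, reconciled to the list | No |

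The elements that protect against foreknowledge are present. Those that would reveal a redraw are not.

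**Mapping from number to arm.** Section 11a, under Preoperative evaluation, defines Group A as CAF with SCTG alone. The Surgical protocol and PRF preparation parts of section 11 make group A the PRF group. A number that resolves to A is therefore ambiguous.

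**Size if two patients change places.** Let their expected reductions differ by δ. Each arm mean moves by δ/17, in opposite directions, so the difference between arms moves by 2δ/17.

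| δ assumed | Shift | Share of 0.45 mm |
|---|---|---|
| 0.38 mm | 2 × 0.38 / 17 = 0.045 mm | 10% |
| 0.5 mm | 2 × 0.5 / 17 = 0.059 mm | 13% |
| 1 mm | 2 × 1 / 17 = 0.118 mm | 26% |

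The documents give no δ. If 0.38 mm is the SD of individual reductions, two random patients differ with SD 0.38 × √2 = 0.54 mm. A gap of 1 mm or more then occurs in about 6% of pairs under normality, so the last row is an extreme case.

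**Size if envelopes are redrawn.** Assume 17 + 17 envelopes picked without replacement and 17 of the 34 patients judged favourable. Someone prefers favourable patients in the test arm and the others in the control arm, and an unwanted first pick is redrawn at most once. By simulation, favourable patients divide between test and control as follows.

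| Unwanted first picks redrawn | Test / control split |
|---|---|
| None | 50 / 50 |
| 10% | 53 / 47 |
| 25% | 56 / 44 |
| 50% | 63 / 37 |
| 100% | 76 / 24 |

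Arm sizes end at 17 and 17 in every row, so arm counts alone would not reveal redraws. The first row confirms that an undisturbed pick is balanced on average.

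**The case against.** The strongest reply is that the sections can be read together: the computer output fills the envelopes, an independent person prepares them, and the participant draws one. On that reading the draw is a valid random permutation, and its independence of enrolment order is not itself a source of bias. This stands. Steering the pick would need knowledge of what is inside an opaque sealed envelope, and nothing in the documents suggests that anyone has it. Revealing the group late also helps, because consent, eligibility and baseline measurement come first.

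A reader might go further and infer that the plan has three rival sources of assignment, that no record exists, that tampering would leave no trace, or that the comparison is biased. The documents do not support any of these. Sections 16 and 16b are compatible, and only the pick is out of line with section 16. The plan is silent about a log, which is not a statement that none will be kept. No irregular allocation is described.

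What the reply does not meet is the redraw. Opacity and seals work until the envelope is opened, and independence in preparing the sequence does not govern what happens at the draw.

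**Conclusion.** The point holds as a weakness in verifiability. The participant's pick does not fit section 16, is not tied to enrolment order, and comes with no stated means of confirming that the first envelope opened was the one used. The realistic exposure is a redraw after opening, with operator and participant unblinded.

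Each exchange would shift the primary difference by 0.045 to 0.12 mm, or 10% to 26% of the target, for patients 0.38 to 1 mm apart. That range rests on 17 analysed per arm, on ±0.38 mm being an SD at its lower end, and on an unsourced 1 mm at its upper end. A reader might take 26%, or twice that for two exchanges, as the expected bias. It is not, because the documents give no frequency for such exchanges and a 1 mm gap is unusual. The plan should be changed because a better procedure costs little.

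**What to change.** - In section 16a, delete the sentence that has the participant pick the number.
- State that the independent person in section 16b fills sequentially numbered, opaque, sealed envelopes from the computer list.
- Open each envelope in strict enrolment order after baseline measurements. Log patient ID, envelope number, date and time, and later reconcile the log to the list.
- Align sections 16, 16a and 16b, including who holds and releases the envelopes.
- Reconcile the group A and B labels across section 11 so that each number maps to one arm.

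The sample size and the treatments do not change. The independent person must hold or release envelopes at 34 allocations, and the plan does not show that this person will be available for that. With a fixed 17:17 list the last assignments may become predictable to an unblinded operator, but the same is true of a draw from 17 + 17 envelopes.

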**16b-Implementation:**

- All patients who give consent for participation and who fulfill the inclusion criteria will be randomized.
- Randomization will be performed by [name] who is neither involved in the treatment nor in the outcome measurements.

**17-Blinding**

- Blinding of the participants and operator is not applicable because of the nature of the treatment.
- Outcome assessor will be blinded.
- The biostatistician will be blinded.

**18-Data collection methods****18a-Data collection method:**

The phone numbers and address of the patient included in the study will be recorded from them or extracted from the patient's file which will be available at [name] office , the one responsible for filing system in the Oral Medicine and Periodontology department. The data will be collected by dr [name], whether personal or numerical. They will be stored on excel sheets as an electronic copy and printed hardcopy sheets. The outcome data will be collected at 0, 3 and 6 months. Numerical data will be presented as mean and standard deviation

**18b- Plans to promote participant retention and complete follow- up**

- Telephone numbers of all patients included in the study will be recorded as a part of the written consent.
- All patients will be given a phone call at the time of the pre-determined follow up dates.and transportation fees may be offered.

**19- Data management**

- All data will be entered and saved electronically by [name] paper sheets that are concerned with the personal or outcome data will be stored in locked cabinet and in the computer at the Oral Medicine and Periodontology department.

The excel sheets of the patients data will be stored in the computer of the Oral Medicine and Periodontology Department- Faculty of Oral and Dental Medicine

- Patient files are to be stored in numerical order and stored in secured file. Data will be encrypted using a password.
- All data will be maintained in storage for 1 year after completion of the study.

## **20- Statistical method:**

Data management and statistical analysis will be performed using Statistical Package for Social Sciences (SPSS) vs. 21. Numerical data will be summarized using means and standard deviations or medians and ranges. Data will be explored for normality using Kolmogrov-Smirnov test and Shapiro-Wilk test. Categorical data will be summarized as percentages. Comparisons between two groups and over time will be done by 2 way analysis of variance for repeated measures. If the time factor is not considerable, comparisons between the two groups for normally distributed numeric variables will be done using the Student's t-test while for non-normally distributed numeric variables will be done by Mann-Whitney test. A p-value less than or equal to 0.05 will be considered statistically significant. All tests will be two tailed.

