 **The secondary objectives:**

	Outcome name	Measuring Device	Measuring Unit
Primary1ry	Recession depth	William's graduated Periodontal probe	mm
Secondary2ry	Recession width	William's graduated Periodontal probe	mm
	Root coverage gain	William's graduated Periodontal probe	mm
	Probing depth	William's graduated Periodontal probe	mm

		probe	
Clinical attachment level	William's graduated Periodontal probe	mm	
Gingival biotype	William's graduated Periodontal probe	mm	
Width of keratinized gingiva	William's graduated Periodontal probe	mm	
Patient satisfaction	Printed questionnaire Binary ( Zuhr et al.2014 )	Yes/No	
Root coverage esthetic score	Score (Cairo et al. 2009)	Categorical	
Post-Operative Pain	Numerical Rating Scale (NRS) (Breivik et al. 2008)	Numerical	

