#### **12- Outcomes:**

[name] is responsible for measuring all the outcomes and collecting data.

	Outcome name	Measuring Device	Measuring Unit
Primary1ry	Recession depth	William's graduated Periodontal probe	Mm
Secondry2ry	Recession width	William's graduated Periodontal probe	Mm
	Root coverage gain	William's graduated Periodontal probe	Mm
	Probing depth	William's graduated Periodontal probe	Mm
	Clinical attachment level	William's graduated Periodontal probe	Mm
	Gingival biotype	William's graduated Periodontal probe	Mm
	Width of keratinized gingiva	William's graduated Periodontal probe	Mm
	Patient satisfaction	Printed questionnaire Binary (Zuhr et al.2014)	Yes/No
	Root coverage	Score	Categorical

	esthetic score	(Cairo et al. 2009)	
	Post-Operative Pain	Numerical Rating Scale (NRS) (Breivik et al. 2008)	Numerical

The probe is held parallel to the long axis of the tooth. The pressure applied with the probe tip should be between 10-20 grams. Blanching of the gingiva should be avoided.

- Recession depth: from the CEJ to the margin of the gingiva at the midbuccal point of the teeth.
- Recession width: measured horizontally between two borders of the recession
- % of root coverage: (preoperative vertical recession – postoperative vertical recession/preoperative vertical recession) x 100.
- Probing depth: measured from the gingival margin to the base of the pocket probe at the midbuccal point of the teeth.
- Clinical attachment loss: measured from the CEJ to the base of the sulcus at the midbuccal point of the teeth.
- Gingival biotype: under local anesthesia from 3 mm below the gingival margin trans-gingivally piercing tissues horizontally, perpendicular to the long axis of the tooth until it contacts bone.
- Width of keratinized gingiva: from the margin of the gingiva to the mucogingival junction at the midbuccal point of the teeth.
- Patient satisfaction: printed yes/ no questionnaire with 3 questions
- Root coverage esthetic score **(Cairo et al. 2009)**
- Post-Operative Pain: Numerical Rating Scale (NRS) with numbers from 0 to 10 ('no pain' to 'worst pain imaginable') for the first 2 weeks postoperatively. (Breivik et al. 2008)

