### مقياس الألم

اليوم	التاريخ
اليوم (0) يوم العملية	
اليوم (1)	
اليوم (2)	
اليوم (3)	
اليوم (4)	
اليوم (5)	
اليوم (6)	
اليوم (7)	
اليوم (8)	
اليوم (9)	
اليوم (10)	
اليوم (11)	
اليوم (12)	
اليوم (13)	
اليوم (14)	

Filled in by the patient

مقياس رضا المريض بعد اجراء العملية

(1-7)

الاسم:

هل تود ان تجرى لك العملية مرة اخرى ؟

هل تناصح بها للاخرين ؟

الى اى مدى انت راض عن النتائج ؟

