### 3. Root coverage esthetic score

The RES system evaluates five variables 6 months following surgery: gingival margin (GM), marginal tissue contour (MTC), soft tissue texture (STT), mucogingival junction (MGJ) alignment, and gingival color (GC). The clinical esthetic evaluation is performed without magnification. Zero, 3, or 6 points are used for the evaluation of the position of the gingival margin, whereas a score of 0 or 1 point is used for each of the other variables

- GM: -Zero points = failure of root coverage (gingival margin apical or equal to the baseline recession)
  - 3 points = partial root coverage;
  - 6 points = CRC.
- MTC: -Zero points = irregular gingival margin (does not follow the CEJ).
  - 1 point = proper marginal contour/ scalloped gingival margin (follows the CEJ).
- STT: - Zero points = scar formation and/or keloidlike appearance .
  - 1 point = absence of scar or keloid formation.
- MGJ: - Zero points = MGJ not aligned with the MGJ of adjacent teeth.
  - 1 point = MGJ aligned with the MGJ of adjacent teeth.
- GC: -Zero points = color of tissue varies from gingival color at adjacent teeth.
  - 1 point = normal color and integration with the adjacent soft tissues.

Thus, the ideal esthetic score is 10.

Zero points are assigned if the final position of the gingival margin is equal or apical to the previous recession depth (failure of root coverage procedure), irrespective of color, the presence of a scar, MTC, or MGJ. Zero points are also assigned when a partial or total loss of interproximal papilla (black triangle) occurred following the treatment.

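### Do the root coverage esthetic score and patient satisfaction lack a usable group comparison, and is percentage root coverage wrongly defined?

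*Combined protocol and SAP*

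**What the plan says.** Section 20 names three tests. The first is for repeated measurements: "Comparisons between two groups and over time will be done by 2 way analysis of variance for repeated measures". Where time plays no material part, it gives Student's t-test for normally distributed numeric variables, and the comparison "for non-normally distributed numeric variables will be done by Mann-Whitney test". For categorical data it says only "Categorical data will be summarized as percentages".

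The outcome tables in section 7 (secondary objectives) and section 12 enter RES with a score as its measuring device and categorical as its unit. Appendix item 3 describes the instrument: "The RES system evaluates five variables 6 months following surgery". It sets out the points for each variable and ends "Thus, the ideal esthetic score is 10". The timeline in section 13 schedules RES once, at 6 months.

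Satisfaction appears in the tables as "Printed questionnaire Binary" and in section 12 as "Patient satisfaction: printed yes/ no questionnaire with 3 questions". The timeline schedules it once, at 1 month. The third question on the Arabic form in the appendix reads "الى اى مدى انت راض عن النتائج", which asks how far the patient is satisfied with the results.

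Root coverage is a gain in millimetres in both outcome tables. It is a percentage in the definitions below the section 12 table and in the timeline.

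**The concern.** Matching each outcome's stated type to the tests in section 20 leaves two gaps. RES, typed categorical, gets percentages and no test. Satisfaction, typed yes/no, gets the same. Neither is measured repeatedly, so the repeated-measures analysis of variance does not reach them. The general objective in section 7 includes a harmonious appearance, so these are the outcomes a reader would look to for the aesthetic and patient-reported result.

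Three risks follow on that reading. The test might be chosen after the data are seen. If RES were analysed as unordered categories, its ordering would be thrown away and power would fall. A question about degree, answered yes or no, would be hard to interpret. Separately, the root coverage formula as typed divides only the postoperative value, and the outcome carries two different units.

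**Working it through.** **1. The primary analysis is not involved.** Inputs from section 14: difference 0.45 mm, SD 0.38 mm, 80% power, 5% significance; section 20 makes tests two-sided. By the normal approximation,

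n per group = 2 × (1.96 + 0.842)² × (0.38/0.45)² = 2 × 7.85 × 0.713 = 11.2, rounded up to 12.

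This reproduces the plan's 12; the exact t-test solution is 12.23. Nothing in the concern enters this calculation.

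**2. What kind of variable RES is.** Inputs from appendix item 3: the gingival margin earns 0, 3 or 6 points, and four other variables earn 0 or 1 each. Failure of coverage, or loss of the papilla, sets the total to 0.

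- Failure: 0
- Partial coverage: 3 + (0 to 4) = 3 to 7
- Complete coverage: 6 + (0 to 4) = 6 to 10

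The attainable totals are 0 and 3 to 10, nine ordered values in which higher is better. That is a numeric score, and the tables' own device column calls it a score. Because it is taken once, it has no time factor, so the second branch of section 20 applies: check normality, then use the t-test or Mann-Whitney. With nine attainable values and a ceiling at 10, Mann-Whitney is the likely outcome of that check. The only obstacle is one word in a unit column, which the scoring definition overrides.

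**3. Yes/no satisfaction items.** Section 20 names no test for them; this gap is real. The data form a 2 × 2 table with at most 17 patients per row. Fisher's exact test is the usual choice at that size. The percentages that section 20 does promise would be reported in any case.

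**4. Satisfaction item 3.** Its wording asks for a degree, while section 12 describes three yes/no questions. These do conflict. The answer fields cannot be judged from the available text: the pain chart on the same pages shows only day and date and no place for a score, so form content was probably lost in conversion from PDF. If the answers are yes/no, they are handled as in step 3; if graded, Mann-Whitney is available.

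**5. Root coverage.** Write Pre and Post for recession depth before and after surgery.

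- As typed: (Pre − Post/Pre) × 100. This subtracts a pure ratio from a length. With complete coverage (Post = 0) it returns 100 × Pre, which equals 100% only for a 1 mm defect.
- As intended: [(Pre − Post)/Pre] × 100. With Post = 0 this is 100% for every defect.

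The typed version cannot be a percentage of root covered, so no analyst would program it. The millimetre gain is Pre − Post, the numerator of the intended formula and the same quantity as the decrease in recession depth used in section 14. The two labels rest on one set of readings.

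**The case for a change.** The strongest case for a change is that RES is labelled categorical in two tables, so this is not a single typing slip, and that an analyst who has to choose between the label and the scoring definition would be choosing after data collection. For satisfaction, no rereading of section 20 supplies a test. Naming the tests would cost a few words.

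Part of this stands. The label does conflict with the appendix, section 20 is silent on binary data, and item 3 does not match its description. The consequence is small. For RES the choice between the two available tests is already tied to the normality check, and section 17 blinds both the outcome assessor and the biostatistician. For binary items in groups this small, there is little room to steer the result by picking among standard tests. The feared loss of power needs a test for unordered categories, and the plan names none.

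The satisfaction schedule could also be challenged, since section 18a speaks of collecting outcome data at 0, 3 and 6 months. Postoperative pain also falls outside those points, so that sentence reads as a summary of the clinical measurements. The timeline remains the specific schedule and gives the questionnaire one clear time point.

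**Conclusion.** No change to the plan is needed. The points are missing detail and clerical slips on secondary outcomes: a type label that the scoring definition corrects, a standard test left unnamed for yes/no items, one of three questionnaire items worded as a degree, and a bracket and unit inconsistency whose meaning is clear. None alters the primary comparison of recession depth, its test or the planned 17 per group, and none would change the trial's conclusion.

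This rests on two assumptions. The first is that the analyst follows the appendix in treating RES as an ordered score. The second is that item 3 is reported according to the response format actually printed on the form, which cannot be seen here. If that format turned out to be ambiguous, the loss would be confined to one supportive item.

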**- Rationale for carrying out the trial:**

Subepithelial connective tissue graft (SCTG) secured by a coronally advanced flap (CAF) is one of the substantial surgical alternatives and is utilized as often as possible because of its great consistency (**Wennstrom and Zucchelli, 1996; Paolantonio et al., 2002; Tozum and Demiralp, 2003**). However, uncertain complete root coverage (between 18.1 %and 86.7%) has been documented as well as confined regeneration of the lost attachment apparatus with a remedial through long junctional epithelium or adaptation of connective tissue to the root surface after the use of CAF+SCTG (**Cummings et al. 2005**).

One of the enhancers of periodontal tissue regeneration and promoters of early wound healing is found to be the Platelet rich fibrin (PRF) (**Tozüm et al. 2003**). There are only a few reports documenting the use of platelet rich plasma (PRP) in aesthetic periodontal surgery. **Petrungaro (2001)** published a case series in which PRP, SCTG and collagen membranes were used to cover gingival defect. The 2 months study resulted

in 3 mm root coverage. Accordingly, this study will assess the effect of PRF as an adjunct to CAF+SCTG on root coverage outcomes.

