#### **-Aim of the study**

The aim of this randomized controlled clinical trial with a 6 months follow-up is to evaluate the effectiveness of CAF+SCTG+PRF in the treatment of Miller class I and II recession defects and to compare the outcomes to CAF+SCTG alone.

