 **The primary objective:**

Recession depth which will be measured before the surgical procedure, then after 3 and 6 months.

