#### **14 - Sample size**

The aim of this study is to evaluate the use of coronally advanced flap and subepithelial connective tissue graft with or without platelet rich fibrin regarding Recession depth. In a previous study by **Keceli et al., 2015** the expected difference in Recession depth decrease from baseline between 2 groups is  $0.45\pm0.38$ mm. Using power 80% and 5% significance level we will need to study 12 in each group to be able to reject the null hypothesis that the population means of the experimental and control groups are equal. This number is to be increased to 14 in each group to correct for non-parametric usage and increased again to 17 to compensate for possible losses during follow up. Sample size calculation was achieved using PS: Power and Sample Size Calculation software Version 3.1.2 (Vanderbilt University, Nashville, Tennessee, USA ).

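### Section 20 does not say which repeated-measures ANOVA term answers the primary question and does not adjust for baseline recession depth; a 6-month ANCOVA would settle both

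*Combined protocol and SAP*

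**What the plan says.** Section 20 holds the whole analysis plan. Its main sentence is: "Comparisons between two groups and over time will be done by 2 way analysis of variance for repeated measures". It continues: "If the time factor is not considerable, comparisons between the two groups for normally distributed numeric variables will be done" by t-test, with the Mann-Whitney test for variables that are not normally distributed. It names no deciding term, no deciding visit and no covariate.

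The primary objective is "Recession depth which will be measured before the surgical procedure, then after 3 and 6 months", and section 18a agrees: "The outcome data will be collected at 0, 3 and 6 months". The aim sets the horizon: "The aim of this randomized controlled clinical trial with a 6 months follow-up is to evaluate the effectiveness of CAF+SCTG+PRF". The PICOTS list likewise pairs recession depth with 6 months.

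Section 14 rests the sample size on one quantity: "the expected difference in Recession depth decrease from baseline between 2 groups is" 0.45 ± 0.38 mm, giving 12 per group. It then adds: "This number is to be increased to 14 in each group to correct for non-parametric usage", and goes to 17 for losses. The rationale notes that with the comparator procedure "uncertain complete root coverage (between 18.1 %and 86.7%) has been documented".

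**The concern.** A two-way repeated-measures ANOVA returns a group term, a time term and a group-by-time term. Group and group-by-time answer different questions, and section 20 does not choose between them. If baseline is one of the time levels, the group term averages in a visit before treatment, where randomisation makes the expected difference zero. It therefore estimates a diluted effect. Group-by-time is closer to section 14's difference in decrease, but with three visits it is a two-degree-of-freedom test whose power depends on the 3-month effect.

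Two lesser points go with this. Baseline depth is measured but not used as a covariate, which costs efficiency. The clause about the time factor is undefined, yet it is the only route to the Mann-Whitney test. It may be meant for outcomes assessed once: section 13 schedules percentage root coverage and the esthetic score at 6 months only. Since it does not say so, it is unclear whether the primary outcome keeps the non-parametric option for which section 14 raised 12 to 14.

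At stake is whether the reported primary test is the one the trial was sized for.

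**Working it through.** **Inputs.** From section 14: difference 0.45 mm, SD 0.38 mm, 12/14/17 per group, 80% power, 5% level. From section 20: two-sided tests. Assumed, because the documents do not give them: normal data, equal visit SD S, a common correlation ρ between visits (0.2/0.5/0.7), and the full effect at both 3 and 6 months unless stated. Section 14 does not say what 0.38 mm is the SD of, so both readings are shown.

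**The plan's own figure.** n = 2(1.96 + 0.842)²(0.38/0.45)² = 11.19, so 12 per group. This is a two-sample comparison of means. By the exact t-test, power is 79.2% at 12, 85.4% at 14 and 91.7% at 17.

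**Visit SD at ρ = 0.2/0.5/0.7.**
- Reading A, 0.38 is the SD of change: S = 0.38/√(2(1−ρ)) = 0.300/0.380/0.491.
- Reading B, 0.38 is the visit SD: S = 0.38, so the SD of change is 0.38√(2(1−ρ)) = 0.481/0.380/0.294.

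**Formulas at n = 14 per group.**
- Group term: effect (0 + 0.45 + 0.45)/3 = 0.30 mm; variance of a patient's mean S²(1+2ρ)/3; noncentral t, 26 df.
- Group-by-time: noncentral F, 2 and 52 df, λ = (n/2)Σd²/(S²(1−ρ)). The deviations d are −0.30, 0.15 and 0.15, so Σd² = 0.135. Under A, S²(1−ρ) = 0.38²/2 = 0.0722 and λ = 7 × 0.135/0.0722 = 13.09 at any ρ. With half the effect (0.225 mm) at 3 months, Σd² = 0.10125 and λ = 9.82.
- Change-score t-test: SE = SD of change × √(2/14), 26 df.
- 6-month ANCOVA: residual SD = S√(1−ρ²); SE = residual SD × √((2/n)(1 + 1/(2n−4))); 25 df. The 3-month effect does not enter.

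**Power (%) at ρ = 0.2/0.5/0.7.**

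| Test | A: 0.38 is SD of change | B: 0.38 is visit SD |
|---|---|---|
| Group term, baseline as a level | 96/69/41 | 84/69/61 |
| Group-by-time, full 3-month effect | 89/89/89 | 70/89/99 |
| Group-by-time, half 3-month effect | 78/78/78 | 57/78/95 |
| Change-score t-test | 85/85/85 | 66/85/97 |
| 6-month ANCOVA | 97/93/89 | 85/93/98 |

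Under A the group term drops below 80% once ρ exceeds about 0.41. With half the 3-month effect its expected difference is (0 + 0.225 + 0.45)/3 = 0.225 mm and its power is 80/46/26%.

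**Illustration of a floor at zero.** The rationale's 18.1–86.7% complete coverage means that many 6-month depths may be exactly 0. This was simulated at 14 per group under reading A, with an assumed mean baseline of 3.0 mm, depth cut off at 0, and 18.1% or 50% of control depths at 0.

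| Test | 18.1% zeros | 50% zeros |
|---|---|---|
| Change-score t-test | about 50 | about 15 |
| Mann-Whitney on 6-month change | 45/47/49 | 13/13/14 |
| Mann-Whitney on 6-month depth | 93/79/59 | 79/63/45 |
| ANCOVA | 91/85/79 | 66/58/50 |
| Rank ANCOVA | 93/87/81 | 79/70/60 |

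Group-by-time, which also works on change, gives 55/57/58% and 19/19/19%. The floor shrinks the observed effect itself, so none of these figures predicts the trial's power.

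**The case against.** The strongest reply is that the plan can be read sensibly. Section 14 concerns a difference in decrease from baseline. In a group-by-time ANOVA that includes baseline, this is what the interaction captures, and under reading A it has 89% power at 14 per group. A reader might infer that the trial is underpowered as planned. The documents do not support that: the sharp loss needs the group term, baseline entered as a level, and a correlation that they do not give.

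A reader might also infer a type I error near 10%, from 1 − 0.95² = 9.75%, if either term could count as success. Section 20 states no such rule, so this is not a consequence of the plan. Nor is the 6-month horizon missing: the aim and PICOTS give it, and section 20 only fails to repeat it. Leaving out the covariate is inefficient, not wrong.

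The floor results cannot firmly rank the tests. The 3.0 mm baseline, the cut-off at zero and the constant shift are all assumed. With depth rounded to whole millimetres, 18.1% zeros and ρ = 0.2, the group term beat ANCOVA (48% v 32%), a reversal that itself depends on the assumed baseline mean. Rank ANCOVA also beats ordinary ANCOVA in both floor settings shown.

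All of this stands. It leaves untouched that section 20 does not name the deciding term and that its switch to simpler tests is undefined.

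**Conclusion.** The point holds as an incomplete specification that should be fixed, with a better method available from data already planned. That section 20 names no deciding term and no baseline adjustment is certain from the text and rests on no assumption.

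The size is conditional. At 14 per group and ρ from 0.2 to 0.7, the choice of term moves power between 41% and 96% under reading A, and between 61% and 99% under reading B (both with the full effect at 3 months). ANCOVA stays at 89–97% and 85–98%. It does not depend on the 3-month effect and is at or near the best in each case. These figures assume normal data, equal visit SDs and a common correlation. The floor figures are illustrations only. They justify a rank-based check on 6-month depth and caution against one based on change.

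**What to change.** In section 20, with the sponsor confirming 6 months as the deciding visit:

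1. Primary analysis: ANCOVA of 6-month recession depth, with group as factor and baseline depth as covariate, two-sided 0.05, reporting the adjusted difference and its 95% CI.
2. Make the 3-month comparison and the repeated-measures ANOVA secondary.
3. Prespecify a rank-based sensitivity analysis on 6-month depth: rank ANCOVA (ranked depth on ranked baseline) or Mann-Whitney on 6-month depth. Do not base it on change. This also gives section 14's non-parametric allowance a defined use.
4. Replace the clause about the time factor with a statement that the t-test or Mann-Whitney test applies to outcomes measured at a single visit.

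The cost is a few sentences and one degree of freedom, with no new data, visits or patients. The trade-off is that group-by-time can equal or slightly beat ANCOVA when ρ is about 0.7 or higher and the full effect is present at 3 months. Under reading A both give 89% at ρ = 0.7, and it is 89% against 86% at ρ = 0.9. A 6-month change-score t-test would match section 14 and also name a single test, but it has less power than ANCOVA over the range shown and loses most of its power in the floor illustration.
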